Small-quantity lipid-based nutrient supplements (SQ-LNS) belong to a family of products that deliver vitamins and minerals, essential fatty acids, protein and energy in a lipid matrix. They are made from vegetable oil, milk powder, peanut paste, sugar and multiple micronutrients and have been shown to have the potential to improve child growth and development. Between 2009 and 2014, the International Lipid-based Nutrient Supplements study (iLiNS-DYAD trial) was conducted in Ghana to examine the efficacy of SQ-LNS for pregnant and lactating women. 1320 pregnant women ≤20 weeks gestation were enrolled and individually randomized to receive daily, either (a) 60 mg iron plus 400 µg folic acid during pregnancy, and a calcium placebo during the first 6 months postpartum, with no supplementation for offspring during infancy (IFA group) or (b) 1-2 RDA of 18 micronutrients during pregnancy and the first 6 months postpartum, with no supplementation for offspring during infancy (MMN group) or (c) small quantity lipid-based nutrient supplements (20 g) which contain 22 micronutrients plus some macronutrients, during pregnancy and the first 6 months postpartum, with SQ-LNS for offspring from 6 to 18 months (LNS group).

The SQ-LNS have a moderately sweet taste due to the sugar and milk they contain, and concern has been raised regarding their potential to impact sweet taste preference in children later on in life, given how long the children were exposed to the supplement during the study. Given that children are born with an innate preference for sweet foods, and also that the 20g SQ-LNS contains very little added sugar and also forms only a small percentage of the sweet food intake of this population, we do not think SQ-LNS will influence sweet taste preference. However, given that SQ-LNS is a novel product, it is important that we rule out any negative consequences.

From January to December 2016, we conducted a follow up study of the children (now aged 4-6 years) who participated in the main iLiNS trial with the overall aim of examining the long term impact of the provision of SQ-LNS antenatally and during lactation and infancy on maternal and child health and nutrition outcomes. This SAP describes the non-inferiority analysis to examine the impact of SQ-LNS on child sweet taste preference. We hypothesize that the mean preferred percentage sucrose score of children who were exposed to SQ-LNS in utero, via breastmilk, and from 6 to 18 months of age will not be more than 1.64 % w/v sucrose units higher than that of the non-LNS group.

Specific objective

To examine the impact of early exposure to a small-quantity lipid-based nutrient supplement (SQ-LNS) in utero, via breastmilk, and from 6 to 18 months of age on the sweet taste preference of Ghanaian children aged 4-6 years.

Hypothesis:

1. The mean preferred percentage sucrose score of children who were exposed to SQ-LNS in utero, via breastmilk, and from 6 to 18 months of age will not be more than 1.64 % w/v sucrose units higher than that of the non-LNS group.

Study population, design inclusion and exclusion criteria

This study is a follow-up to the main iLiNS-DYAD trial. All women and children who participated in the main trial (except those who reported miscarriages) were eligible to be included in the follow-up study, irrespective of whether or not they remained in the main trial at endline (women, 6 mo postpartum; children, 18 mo of age). Based on our study objectives, and because we were only interested in the impact of SQ-LNS and not in comparing IFA and MMN groups, we will combine the IFA and MMN groups and compare:

- 1. Children who were exposed to SQ-LNS in utero, through breastmilk (up to 6 mo postpartum), and from age 6 to 18 months (LNS group).
- 2. Children who were never exposed to SQ-LNS: their mothers received IFA/MMN (non-LNS group).

For this present analysis, a subsample of mother-child dyads were randomly selected from among the total sample that were eligible for the follow-up study. The selection was done such that in the non-LNS group, we had equal numbers of children from the IFA and MMN groups.

Blinding

All data collectors and study investigators were blinded to the assigned treatment group. This statistical analysis plan was written before the start of any analysis. All investigators who will be running any analysis will remain blinded until initial analysis of primary outcomes is complete.

Outcome

Sweet taste preference

Our main outcome is child sweet taste preference, defined as the mean percentage sucrose score on the Monell Forced Choice taste test (1).

Statistical analysis

Analysis principles

- 1. Analysis will be by intention-to-treat. Results will be analyzed according to the group to which participants were assigned regardless of whether they got the treatment or if they followed protocol.
- 2. Data for all participants who were lost to follow-up because of death, refusal to continue with the study, or travel from study site will be included in the analysis of household and maternal baseline characteristics, if available.
- 3. Outcomes will be compared between groups using non-inferiority hypothesis testing.
- 4. Sweet taste preference scores will be compared between study groups using a non-inferiority margin of 1.64 w/v, which corresponds to an effect size of 0.2.
- 5. Analysis of treatment effect will be done using negative binomial models. The negative binomial modelling technique outputs differences between groups as ratios or percentage difference instead of mean difference. To make comparisons more efficient and easy to understand, we will convert the non-inferiority margin from the absolute value of 1.64 to a ratio (or percentage difference) by dividing 1.64 by the mean preference score of our sample. Comparisons between groups will be made using this ratio as our non-inferiority margin.
- 6. Tests will either be one-sided (main outcome comparisons) or two-sided (baseline comparisons) and at 5% level of significance, except as otherwise stated.
- 7. In reporting our results, we will report the number of observations used in the analysis wherever there are more than 10% of observations missing for a dependent or outcome variable.
- 8. In addition to the intention-to-treat analysis, we will conduct other analysis by re-running the final models in pre-specified sub-samples described below:
 - We will re-run the analysis excluding those children whose preferred sucrose solutions for series 1 and series 2 were > 2 concentrations apart.

Sample size

The subsample size was calculated based on the primary objective: to test the hypothesis of non-inferiority of SQ-LNS regarding long term sweet taste preference as compared to no LNS. The null hypothesis is that the difference in preference score between the LNS and non-LNS group will be 1.64 % w/v or more (non-inferiority margin).

A pilot study in the study area showed the preferred percentage sucrose solution score to be 15.7 ± 8.2 %. Assuming a standard deviation of 8.2 percent sucrose and a pre-determined non-inferiority margin of 1.64 percent sucrose w/v (an effect size of 0.2), a sample size of 620 was estimated to provide the trial with 80% power and 95% confidence to discard the inferiority null hypothesis. Adjusting for 15% attrition rate (including child deaths, loss to follow-up, refusals) brings the total sample size to 713 (356 participants per group).

Study flowchart

A participant flow diagram will be prepared in accordance with the CONSORT 2010 guidelines. The figure (Figure 1 below) will include the numbers and reasons for permanent loss to follow up between the start of the main trial and end of the follow-up study.

Data cleaning

Data cleaning for this follow-up study was done alongside data collection. Range checks were built into direct data entry by enumerators. SAS syntax were written and run weekly to generate a list of queries on plausible but extreme values or inconsistent responses, which were then examined and resolved with the help of the field worker. The corrections/ changes were then recorded in a "data cleaning excel sheet" which was used to generate additional syntax and a corrected data set.

Outliers

Data will be visually examined by means of histograms (for individual continuous variables) and scatter plots (of related variables) to check for outliers after which they will be investigated. Outliers which are clearly implausible or impossible will be corrected if possible or recoded to missing where correction is not possible. Those that are plausible or possible will be kept in the dataset. During analysis, we will transform variables with outliers, and if needed, we will conduct sensitivity analysis by running the models with and without these outliers to examine if these outliers have undue influence on the results.

Software for analysis

All analyses will be done using SAS version 9.4 (SAS Inst. Cary, NC, USA).

Baseline characteristics of participants and baseline comparisons

Baseline characteristics will be compared between groups using ANOVA for continuous variables or a chisquare test for categorical variables. If there are dropouts (selected for the subsample but who were not
tested for various reasons), we will compare baseline characteristics between participants who will be
included in the analysis and the dropouts. Baseline characteristics will be selected household and
maternal characteristics at baseline, that is, all available values for these selected variables at the time of
maternal enrolment into the main study, prior to first intake of study supplement. Child age will however
be the age of child at the time of sweet taste preference testing. In analyzing baseline characteristics:

[figure not shown]
- Means and SE (or SD) or medians and 25th and 75th percentiles will be used to describe continuous data.
- 2. Frequencies and percentages will be used to summarize categorical data. We will calculate percentages based on the number of participants for whom data are available.
- 3. Where data for certain participants are missing (>10 %), the number of participants included in the analysis will be indicated.

Analysis of the impact of the intervention

Negative binomial models will be used to test the null hypothesis of inferiority between the two groups. We will first run the models without covariates, then run them again controlling for pre-specified covariates. Only covariates significantly associated with the outcome at 10% level of significance in bivariate analysis will be included in the final adjusted analysis. Results will be presented as the difference

in means between the two groups. The 95% confidence interval will be reported. Results will be interpreted as follows (and graphed below):

- 1. If the entire 95% CI is below the non-inferiority margin, we conclude that **non-inferiority** has been established
- 2. If the lower level of the 95% CI is greater than the non-inferiority margin, we conclude that the treatment group is **inferior** (worse in sweet taste/ have higher preference for sweet taste) to the control group.
- 3. If the upper level of the 95% CI is greater than the non-inferiority margin and the lower level is less than the non-inferiority margin, we conclude that the result is **inconclusive**.

Difference in preferred percent sucrose score (LNS group vs. non-LNS group)

Potential covariates

Independent of the intervention, child sweet taste preference could be influenced by a variety of household, maternal, and infant factors. Each pre-specified covariate (listed below), will be examined for completeness of data, and a decision will be made for the exclusion of any covariate with a high proportion of missing data. Potential covariates that will be examined include:

- Maternal years of formal education
- Maternal estimated pre-pregnancy BMI
- Maternal marital status
- Maternal age
- Parity
- Child age at testing
- Child sex
- Household Assets Index (baseline)
- Household food insecurity index (baseline)
- Distance to market
- Ethnicity

Data transformations

We will examine the residuals of continuous outcome variables to assess if they conform to the normal distribution using the Shapiro-Wilk test. Shapiro-Wilk statistic values >0.97 will be considered acceptable. Any continuous outcome whose residuals are not normally distributed will be transformed appropriately.

Figures and Tables

The following figures and tables are only drafts. They will be examined and final decisions on presentation of information will be made by the manuscript writing group later.

Figures:

Figure 1 will be the study flow chart (shown below) and figure 2 will be the non-inferiority graph shown above.

Figure 1: Study Flow chart

Tables

Variable ³	LNS	No LNS
Number of participants		
Maternal age (y)		
Maternal education (y)		
Married or cohabiting (%)		
Maternal pre-pregnancy BMI (kg/m²)		
Parity (#)		
Ethnicity (%)		
Child male sex (%)		
Child age at follow-up (mo)		
Household Assets Score (#)		
Household Food Insecurity Score (#)		
Distance to market (#)		

²LNS=lipid-based nutrient supplement; Non-LNS = exposure to IFA/MMN but no LNS

³Data will be presented as mean ± SD or Median (Q1, Q3) depending on the distribution

Variable ²	LNS	Non-LNS	P-Value ³
Total time required			
Series 1			
Series 2			
Number of pairs (trials) required to reach criterion			
Series 1			
Series 2			
Both series			
Agreement between series 1 and 2 [n (%)]			
Preferred same solution			
Preferred one concentration higher/lower			
Preferred two concentrations higher/lower			
Preferred more than two concentrations higher/lower			

¹LNS=lipid-based nutrient supplement; Non-LNS = exposure to IFA/MMN but no LNS

²Data will be presented as mean ± SD or Median (Q1, Q3) depending on the distribution

³Differneces between groups will be tested using ANOVA or the chi-squared test for continuous and categorical variables, respectively

Table 3: Preferred sucrose concentration, by intervention group¹

	LNS	Non-LNS	LNS vs. No LNS Difference in means (95% CI) ²
Intensity of sucrose most preferred			
Unadjusted			
Adjusted			

¹LNS=lipid-based nutrient supplement group; Non-LNS = exposure to IFA/MMN but no LNS

REFERENCE

²Differneces between groups will be tested using the negative binomial regression method

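### The primary decision is made on a ratio against a margin derived from the outcome, while the hypothesis, sample size and reported interval are on the difference scale

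*SAP*

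**What the plan says.** Two scales are in use for the one main outcome.

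**Difference in means.**
- The Hypothesis section says that the LNS mean "will not be more than 1.64 % w/v sucrose units higher than that of the non-LNS group".
- The Sample size section gives the null on the same scale: "The null hypothesis is that the difference in preference score between the LNS and non-LNS group will be 1.64 % w/v or more". It derives 620 children from a "pre-determined non-inferiority margin of 1.64 percent sucrose w/v (an effect size of 0.2").
- Under Analysis of the impact of the intervention, the SAP says "Results will be presented as the difference" in means, and rules 1 to 3 compare a 95% CI with the margin. The label of the non-inferiority graph (Figure 2) is a difference in score.
- The results column of Table 3 is headed "LNS vs. No LNS Difference in means (95% CI"), with a footnote that names negative binomial regression as the test.

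**Ratio.**
- The same impact section says "Negative binomial models will be used to test the null hypothesis of inferiority between the two groups".
- Analysis principles, item 5, notes that this model yields ratios or percentage differences. It converts the margin "by dividing 1.64 by the mean preference score of our sample" and concludes: "Comparisons between groups will be made using this ratio as our non-inferiority margin".

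**The concern.** A fixed absolute margin and a ratio margin define different null hypotheses unless the reference mean is known. The model ratio is the LNS mean over the non-LNS mean, so the counterpart of +1.64 is 1 + 1.64/(non-LNS mean). Item 5 uses the mean of everyone tested, LNS children included. If LNS raises sweet preference, it raises that mean and shrinks the margin against which it is judged. A margin that the Sample size section treats as settled beforehand thus depends on the outcome.

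Three things are at stake: whether the test addresses the stated hypothesis, whether the interval in Table 3 and Figure 2 is the one behind the conclusion, and whether the stated 80% power applies to the test that will be run.

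**Working it through.** **Inputs.** From the SAP, Sample size: margin 1.64, SD 8.2, pilot mean 15.7, 620 children (310 per group), 80% power. From Analysis principles, item 6: one-sided 5% for the main outcome. Assumptions of this check: a true difference of 0 for power (the SAP does not state one), a non-LNS mean equal to the pilot mean, and equal group sizes.

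**1. The plan's own figure.** On the difference scale, n per group = 2 × [8.2 × (1.645 + 0.842)/1.64]² ≈ 310, or 620 in total, with power 80.1%. The stated number is reproduced, and it rests on a one-sided 5% test of a difference in means.

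**2. Boundary implied by item 5.** Let C be the non-LNS mean and d the true difference. The whole-sample mean is C + d/2, so the rule's boundary solves d = 1.64 × C/(C + d/2). This gives d = −C + √(C² + 2 × 1.64 × C).
- C = 15.7: d = −15.7 + √297.99 = 1.562, about 5% below 1.64.
- C = 10: 1.52. C = 20: 1.58.

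**3. Direction of the shift.** The absolute equivalent of the margin at C = 15.7 is 15.7 × 1.64/(15.7 + d/2), with d now the observed difference:

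| Observed d | Sample mean | Ratio margin | Equivalent, % w/v |
|---|---|---|---|
| −0.82 | 15.29 | 1.1073 | 1.68 |
| 0 | 15.70 | 1.1045 | 1.64 |
| +0.82 | 16.11 | 1.1018 | 1.60 |
| +1.64 | 16.52 | 1.0993 | 1.56 |

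**4. Error rate at a true difference of 1.64.** Φ[(ln 1.0993 − ln 1.1045)/SE − 1.645], with SE of the log ratio about 0.040 to 0.042, is about 3.9%. In 200,000 simulated negative binomial trials (dispersion set to give mean 15.7 and SD 8.2, and treated as known) the rate was 4.1%, against 5.1% for the test on the difference scale.

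**5. Power at no true difference.** SE of the log ratio = (8.2/15.7) × √(2/310) = 0.04195. The log margin is ln(1 + 1.64/15.7) = 0.0994, against 0.1045 unlogged. Power = Φ(0.0994/0.04195 − 1.645) = 76.5%. About 342 per group (684 in total) would restore 80%. Simulated power was:
- difference scale: 80.3%
- ratio, whole-sample mean as denominator: 76.7%
- ratio, fixed 15.7 as denominator: 76.7%
- ratio, non-LNS mean as denominator: 77.8%

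The loss therefore comes mainly from the log-ratio scale and hardly from the denominator.

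**6. Where the conclusions differ.** With 310 per group, SD 8.2 and a non-LNS mean of 15.7, SE of the difference = 8.2 × √(2/310) = 0.659. At one-sided 5% the difference test passes up to an observed 1.64 − 1.645 × 0.659 ≈ 0.556. The item 5 test passes up to about 0.477. For instance, an observed +0.50 has an upper bound of 1.58 (below 1.64) on one scale and 1.1044 (above 1 + 1.64/15.95 = 1.1028) on the other. The zone is about 0.08 % w/v wide, or 0.079/0.659 = 0.12 SE.

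**The case against.** Several stronger readings are tempting, and the document does not support them.

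- **No scale is named as decisive.** Item 5 does name one, the ratio. What is wrong is that the impact section, its graph and Table 3 do not follow it.
- **A margin of about 0.10 is to be compared with a ratio near 1.** Item 5 speaks of a ratio or a percentage difference, and 1.64/15.7 = 10.4% is a sensible percentage difference. The wording is loose, no more.
- **The margin is always stricter.** It is stricter only when the observed LNS mean is higher. It is exact at equal means and slightly looser when the LNS mean is lower. At the boundary, where the decision is made, the effect is conservative, so a false claim of non-inferiority becomes less likely there.
- **The choice of denominator costs the power.** Step 5 shows otherwise.
- **The two scales will often disagree.** The zone is narrow. The +0.50 example lies inside it and uses a one-sided 5% bound, that is, the upper limit of a two-sided 90% interval. If the 95% CI in rules 1 to 3 is two-sided, both scales fail at +0.50, and the zone moves to about 0.27 to 0.35.

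It is also fair to say that the conversion rule is pre-specified, that analysts stay blinded through the initial primary analysis, and that the whole-sample mean needs no group labels. This protects against choosing the margin to suit the result. It does not make the ratio test a test of the stated hypothesis.

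**Conclusion.** The point stands. The rule in item 5 tests something other than a difference of 1.64 % w/v, and the interval to be shown is not the one that decides. With a non-LNS mean of 15.7, the effective boundary is about 1.56 and the error rate at a true +1.64 is about 3.9% to 4.1%. Separately, power at 310 per group and no true difference is about 76.5%, not 80.1%. With SD held at 8.2, the formula gives 74.6% at a mean of 10 and 77.3% at a mean of 20.

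These effects are modest, and the one on the boundary is conservative. The case for correction is that this is the sole main outcome and its test, margin and reported estimate should agree.

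The power figures assume the one-sided 5% test. If the 95% CI is two-sided, they are 70.2% on the difference scale and 65.8% on the ratio scale. The mismatch between a one-sided 5% test and a 95% CI is a separate matter.

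**What to change.** **Preferred.** Delete the margin conversion from item 5. Obtain the LNS minus non-LNS difference in mean % w/v with its CI, either from standardised means of the negative binomial model (delta-method or bootstrap interval) or from a linear model with robust standard errors. Compare that one interval with the fixed 1.64 in rules 1 to 3, and show the same interval in Figure 2 and Table 3. This matches the scale of the hypothesis and of the sample size calculation.

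**If the ratio is kept.** Fix the margin in advance at 1 + 1.64/15.7 = 1.104, restate the hypothesis as a ratio, put Table 3 and Figure 2 on the ratio scale, and restate the power as about 76.5%. Changing the denominator alone does not restore 80%. A fixed ratio also equals 1.64 % w/v only if the non-LNS mean is near 15.7: at a mean of 20 it would be 0.1045 × 20 = 2.09.

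**Cost.** SAP wording and a few lines of code. No new data are needed.

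### The 15% attrition allowance was added to 620 (620 × 1.15 = 713) when it should have divided it (620/0.85 ≈ 730), so 713 selected children leave about 606 evaluable: a minor shortfall to restate

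*SAP*

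**What the plan says.** The calculation is in the SAP's Sample size section. Its inputs are "Assuming a standard deviation of 8.2 percent sucrose and a pre-determined non-inferiority margin of 1.64 percent sucrose w/v (an effect size of 0.2"), from which "a sample size of 620 was estimated to provide the trial with 80% power and 95% confidence to discard the inferiority null hypothesis". The null hypothesis is given as "The null hypothesis is that the difference in preference score between the LNS and non-LNS group will be 1.64 % w/v or more". No true difference under the alternative is stated.

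The significance level is set in item 6 of Analysis principles: "Tests will either be one-sided (main outcome comparisons) or two-sided (baseline comparisons) and at 5% level of significance".

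The allowance for losses follows: "Adjusting for 15% attrition rate (including child deaths, loss to follow-up, refusals) brings the total sample size to 713 (356 participants per group"). The formula is not shown, and no other part of the SAP gives a different attrition rate or another derivation of 713.

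Two other places matter. The section on baseline characteristics treats as dropouts those children who were chosen for the subsample and then not tested. The study population section describes the selection of the subsample as already done, with IFA and MMN contributing equally to the non-LNS group.

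**The concern.** An attrition rate is a proportion of the children who start, here those selected for testing. The SAP lists the causes as deaths, loss to follow-up and refusals, and it counts dropouts among the selected children, so this is the meaning it uses. To keep a required number after a loss of 15%, that number must be divided by 0.85. Multiplying by 1.15 takes the 15% of the smaller, evaluable number, and so always gives too few.

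The stated target therefore does not meet the stated requirement under the SAP's own attrition assumption. The 620 has almost no reserve (its power is 80.1%), so any shortfall takes the planned power below the 80% claimed. What is at stake is the accuracy of the planning statement: someone reading the eventual result, particularly an inconclusive one, should have the right expected number and power to set it against.

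**Working it through.** **Inputs**

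- SD σ = 8.2 and margin Δ = 1.64, so Δ/σ = 0.2 (Sample size section).
- Power 80% and 620 children evaluable (Sample size section).
- One-sided α = 0.05 for the main outcome (Analysis principles, item 6).
- Attrition 15%; 713 selected, 356 per group (Sample size section).
- True difference 0. This is an assumption, since the SAP states none; it is the value that reproduces 620.

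**Step 1. Reproduce 620.**

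n per group = 2(z₀.₉₅ + z₀.₈₀)² / (Δ/σ)² = 2(1.645 + 0.842)² / 0.04 ≈ 309.1, rounded up to 310. The total is 620, an exact match. With one-sided 0.025 the result would be 393 per group, 786 in total, so 620 does rest on one-sided 5%.

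**Step 2. Reproduce 713.**

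620 × 1.15 = 713.0, an exact match. The allowance was applied by multiplication.

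**Step 3. Apply 15% attrition to the number selected.**

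- 713 × 0.85 = 606.05 evaluable; 620 − 606.05 ≈ 14 short.
- 712 (2 × 356) × 0.85 = 605.2 evaluable; about 15 short.
- Attrition that 713 can absorb: 1 − 620/713 = 13.0%.

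**Step 4. The number that would retain 620.**

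620/0.85 = 729.4, so 730 in total, which is 17 more than 713; check: 730 × 0.85 = 620.5. Two equal groups of 365 would leave an odd non-LNS group, which cannot be divided equally between IFA and MMN. With that constraint the figure is 366 per group (183 + 183 in the non-LNS group), 732 in total.

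**Step 5. Power at the reduced number.**

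Power = Φ( (Δ/σ)·√(n/2) − 1.645 ), with n per group:

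| Evaluable | n per group | Argument of Φ | Power |
|---|---|---|---|
| 620 | 310 | 0.2 × √155 − 1.645 = 0.845 | 80.1% |
| 606 | 303 | 0.2 × √151.5 − 1.645 = 0.817 | 79.3% |

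The loss is about 0.8 percentage points. The noncentral t gives 80.0% and 79.2%, the same loss.

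**The case against.** The strongest reply is that the error makes no practical difference, and most of that reply stands.

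- **The size is trivial.** A power loss of 0.8 points is well inside the uncertainty of the inputs. With 310 per group and an SD of 8.3 in place of 8.2, power is Φ(1.64/(8.3 × √(2/310)) − 1.645) = Φ(0.815), about 79.2%. A shift of 0.1 in a pilot SD costs as much as the whole arithmetic slip. The calculation also compares means under normal theory, whereas the analysis is to be negative binomial with the margin turned into a ratio, so fractions of a point should not be read closely.
- **Nothing can be changed now.** The subsample has been selected. The flow diagram and the comparison of tested children with dropouts will show the actual losses, and the confidence interval will govern interpretation.

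Both arguments bear on severity. Neither makes 713 the right figure for 15% attrition, and the exact match to 620 × 1.15 rules out rounding as the explanation.

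A reader might also infer more than the SAP supports:

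- **That the attrition step takes power to about 69%.** That figure arises only if non-inferiority is judged by a two-sided 95% interval while the size was set at one-sided 5%. Power under that rule is already about 70% at the full 620. Attrition adds about one point, and the rest is a separate question.
- **That 356 per group against 713 is a second error.** Half of 713 is 356.5, so the one-child difference is rounding.

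**Conclusion.** The point holds, and it is minor. The 15% allowance was computed as 620 × 1.15 when it should have been 620/0.85. As written, 713 selected children cover 13.0% attrition. At the stated 15% they leave about 606 evaluable, about 14 below the requirement, with power of about 79.3% against 80.1% at 620.

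The evaluable numbers follow from the SAP's own figures, provided that attrition means a share of those selected, as the SAP's description of dropouts indicates. The power figures rest further on SD 8.2, margin 1.64, one-sided 5%, equal groups, a normal approximation and a true difference of 0, the last being assumed because none is stated.

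It does not follow that the study is materially underpowered because of this step, or that more children should be sought.

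**What to change.** Correct the sentence in the Sample size section in one of two ways:

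1. Keep the 15% rate and state that 712 to 713 selected children would leave about 606 evaluable, with about 79% power at one-sided 5% (true difference taken as 0).
2. Keep 713 and 80% power, and state that this number allows for 13% attrition.

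If the number that would have preserved 620 at 15% attrition is mentioned, give it as 730, or as 732 (366 per group) where the non-LNS group is to divide equally between IFA and MMN. No further recruitment is suggested.

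The cost is a wording change to one sentence. Under the first option the stated power becomes slightly less favourable; under the second the stated tolerance for losses does. The analysis itself is untouched.

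### A count model is planned for a sucrose concentration; it does not match the absolute 1.64 margin, the sample size or Table 3, though in % w/v the effect is modest

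*SAP*

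**What the plan says.** The Outcome section gives the endpoint: "Our main outcome is child sweet taste preference, defined as the mean percentage sucrose score on the Monell Forced Choice taste test". The pilot result in the Sample size section, "the preferred percentage sucrose solution score to be 15.7 ± 8.2" percent, shows that this is a concentration and not a count.

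The model is named in three places: Analysis principles item 5, the section on the impact of the intervention ("Negative binomial models will be used to test the null hypothesis of inferiority between the two groups"), and the footnote to Table 3. No reason is given for a count model, and no robust variance is specified. Item 5 notes the consequence for scale: "The negative binomial modelling technique outputs differences between groups as ratios or percentage difference instead of mean difference". It therefore turns the margin into a ratio by "dividing 1.64 by the mean preference score of our sample".

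Other parts of the SAP work on the absolute scale:
- The hypothesis is a mean difference of no more than 1.64 % w/v.
- The sample size is calculated "Assuming a standard deviation of 8.2 percent sucrose" and an absolute margin of 1.64.
- The impact section and Table 3 report a difference in means with its confidence interval.
- The Data transformations section checks continuous outcomes for normal residuals, which is a linear-model check.

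**The concern.** The negative binomial variance is mu + k·mu². The first term is Poisson noise, which has a meaning only for counts. For a concentration, the balance between the two terms changes with the unit, and a maximum-likelihood k need not reproduce the actual variance of the scores. The model-based standard error then depends on the unit and the shape of the data, and nothing in the plan corrects for this.

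The model also moves the comparison from a difference to a ratio. The study was sized for one test, would be analysed with another, and would be reported on the scale of the first. At stake are the width of the interval that decides non-inferiority and whether the stated 80% power belongs to the planned test.

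**Working it through.** **Inputs from the SAP.** Mean 15.7, SD 8.2, margin 1.64, 620 evaluable (310 per group), 80% power, one-sided 5% for the main outcome (Analysis principles item 6).

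**1. Reproduce 620.** For a difference in means with a common SD:
n per group = 2 × (8.2/1.64)² × (1.645 + 0.842)² = 2 × 25 × 6.18 ≈ 309.1, rounded up to 310, so 620 in total. This matches exactly. At one-sided 2.5% the total would be 786. The sample size is therefore a constant-SD comparison of means; the negative binomial model plays no part in it.

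**2. Effect of the ratio scale alone.** At the pilot mean the margin is 1.64/15.7 = 0.1045, a ratio of 1.1045, with log 0.0994. The log-ratio standard error implied by the pilot figures, in any unit, is √(2/310) × 8.2/15.7 = 0.0420. Power is Φ(0.0994/0.0420 − 1.645) ≈ 76.5%, against 80.1% for the difference in means. About 342 per group (684 evaluable) would be needed for 80%. This loss arises even with a correct standard error.

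**3. Unit dependence.** The model gives SE² = (2/n)(1/mu + k).
- In % w/v, the k that matches the pilot variance is (67.24 − 15.7)/15.7² = 0.209, and SE = √[(2/310)(0.0637 + 0.209)] = 0.0420. A moment-matched k would thus give the right answer; the error comes from the maximum-likelihood k.
- As a fraction, the variance (0.082² = 0.0067) is below the mean (0.157), so k goes to 0 and SE = √(2/(310 × 0.157)) = 0.203.
- In maximum-likelihood fits (150 simulated trials per setting), the mean model SE in % w/v and in g/L was 0.0410 and 0.0418 (gamma), 0.0388 and 0.0387 (log-normal), 0.0446 and 0.0456 (coarse five-step grid), and 0.0453 and 0.0507 (truncated normal).

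**4. Size in the planned unit.** The SAP gives only a mean and an SD, so the shapes are assumptions. SE and power (true difference 0) come from 3000 simulated trials per shape; false non-inferiority (true difference 1.64) comes from 2000. All use 310 per group, one-sided 5%, and margin ln(1 + 1.64/pooled mean) for the negative binomial.

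| Shape | Model SE / empirical SE | Ratio | Power, negative binomial | Power, difference in means | False non-inferiority, negative binomial |
|---|---|---|---|---|---|
| Log-normal | 0.0388 / 0.0422 | 0.92 | 80.3% | 80.6% | 4.8% |
| Gamma | 0.0411 / 0.0420 | 0.98 | 77.7% | 80.4% | 4.9% |
| Bounded 3 to 36 | 0.0436 / 0.0426 | 1.02 | 74.2% | 79.3% | 3.6% |

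For the bounded shape at a true difference of 1.64 the SE ratio was 0.0417/0.0396 = 1.05. A further set of runs put the ratio at about 0.91 to 1.10.

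**5. Separate the two causes.** With the ratio margin kept and only the standard error changed from model-based to robust, power went from 80.8% to 77.4% (log-normal), 78.4% to 77.7% (gamma) and 73.8% to 75.8% (bounded). The count variance thus moves power by about +3, +1 and −2 points. The rest of the shortfall belongs to the margin conversion.

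**The case against.** The strongest reply is that in % w/v the estimated dispersion absorbs most of the misfit. With group as the only term, the point estimate is the ratio of sample means whatever the shape. One sentence adding a sandwich variance would correct the standard error, and sizing a study with a normal approximation while analysing it with a generalised linear model is common practice. All of this stands, and it limits the point to a modest one.

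Three stronger readings are tempting but not supported:
- **That power collapses.** With the score as a fraction, the model SE is about 0.20 against a true 0.042, and simulated power is 0%. But the SAP expresses the score and margin in percent sucrose throughout. The example shows unit dependence; it does not describe a risk of the planned analysis.
- **That the false non-inferiority rate is inflated.** An SE ratio of 0.92 alone would suggest about 6.5%, since 1.645 × 0.92 = 1.51. But at a true difference of 1.64 the pooled mean is 16.52, so the converted margin is ln(1 + 1.64/16.52) = 0.0947, below the true log ratio ln(17.34/15.7) = 0.0994. That stricter margin offsets the short standard error, and the simulated rates were 3.6–4.9%.
- **That the planned power fails because of the count model.** Step 5 shows that much of the loss comes from the ratio margin.

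What the reply leaves unanswered is scale. A sandwich variance repairs the standard error but keeps a ratio test at about 76.5% power, against a hypothesis, a sample size and a results table that are all stated as differences.

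**Conclusion.** The point holds as a modest one that should be corrected. The SAP applies a count model without robust standard errors to a concentration, and that model's output does not match the absolute margin, the calculation behind 620 or Table 3. In the planned unit the standard error is off by up to roughly 10%, in a direction set by the shape of the scores. There is no material inflation of type I error. Power at one-sided 5% is about 74–80%, against about 80% for the difference in means, with part of the loss due to the ratio margin.

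The agreement of 620 with the means formula and the algebra in steps 2 and 3 need only the SAP's own figures. The simulated sizes rest on assumed shapes. In particular, the 3-to-36 bound, which carries the largest power loss, is not in the SAP. The power figures use one-sided 5%, the level that reproduces 620; the SAP's decision rule with a 95% interval is a separate matter and is not counted here.

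**What to change.** Make the primary analysis a linear regression of the % w/v score on group, first unadjusted and then with the covariates, using heteroscedasticity-robust standard errors. Compare the confidence interval for the mean difference directly with 1.64. Remove the ratio conversion from Analysis principles item 5, and amend the model statement in the impact section and the Table 3 footnote to match. Keep the negative binomial model as a sensitivity analysis only, with sandwich standard errors.

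The cost is SAP wording. The test then does not depend on the unit, agrees with the hypothesis, the sample size and Table 3, and has about 80% power at one-sided 5% with 310 per group. In these simulations no power was lost relative to the current plan.
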